8.2 Exclusion Criteria

Subjects who meet any of the following criteria are disqualified from enrollment in the study:

1. Prior participation in this study;
2. A condition that will likely be exacerbated by corticosteroid therapy, including:
 - diabetes mellitus,
 - hypertension,
 - esophageal or gastrointestinal ulceration or bleeding, or
 - known avascular necrosis;
3. Diagnosis of ACS in the 3 months preceding enrollment;

4. Treatment with oral or parenteral corticosteroid therapy for any reason within the preceding 14 days;
5. Use for respiratory illness in the preceding 3 months of:
 - oral corticosteroids, or
 - parenteral corticosteroids;
6. A chronic pulmonary condition that requires treatment with corticosteroids;
7. Current participation in a program of chronic transfusions.
 - “Current participation” denotes that the subject’s last transfusion was given in the 4 months preceding study entry
 - “Program of chronic transfusions” is defined as a regimen of serial simple or exchange transfusions given at least every 6 weeks for at least 3 consecutive transfusions for the prevention of SCD-related complications.
8. Pregnancy;
9. Treatment with any investigational drug in preceding 90 days.
10. A history of either tuberculosis or a positive skin test for tuberculosis;
11. Known infection with HIV or a current systemic fungal infection.

8.3 Stratification

Before randomization, subjects will be stratified by site, age (< 18 years or ≥ 18 years) and by severity of ACS (defined below). Stratification by age and severity of ACS will be done to ensure balance across treatment groups. Strata will not be adequately sized (i.e., powered) to analyze the primary endpoint in each stratum.

Mild to moderately severe ACS is defined by all the diagnostic criteria for ACS listed in the subject eligibility section in addition to the following:

- transcutaneous oxygen saturation of ≥ 85% in room air, and
- segmental or lobar infiltrates that involve no more than two lobes by chest radiography.

Severe ACS is defined by all the diagnostic criteria for ACS listed in the subject eligibility section and one or more of the following:

- impending respiratory failure or need for invasive or non-invasive ventilatory support,

- transcutaneous oxygen saturation of $< 85\%$ in room air or $\leq 90\%$ despite maximal supplemental oxygen, or
- segmental or lobar infiltrates that involve three or more lobes by chest radiography.

8.4 Subject Discontinuation

Subjects may decide to discontinue participation at any time during the study.

Investigators may discontinue any subject at their discretion if, in their professional opinion, the subject's health, safety, and/or well-being is threatened by continued participation in the study. The following circumstances require discontinuation of subjects:

1. New hypertension (not pre-existing) that requires treatment with antihypertensive medications;
2. Stroke;
3. Gastrointestinal hemorrhage; and
4. Pregnancy.

AEs caused by participation in the study may necessitate modifications to a subject's level of participation or discontinuation of subjects from participation in the study.

Subjects who discontinue early from the study will be replaced.

Subjects who discontinue prematurely from the study for any reason will be encouraged to maintain the follow-up clinic visits that are scheduled after discharge. Study personnel will contact subjects by phone to encourage attendance.

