9 TREATMENT OF SUBJECTS

9.1 Treatments

9.1.1 Description of Study Drug and Dosing Regimen

Dexamethasone is a commercially available synthetic corticosteroid hormone that is used primarily as an anti-inflammatory agent. It is available in tablets (several manufacturers), and as a solution for IV injection (several manufacturers).

Potential AEs, especially when given chronically, include hypertension, hyperphagia, weight gain, hyperglycemia, striae, acne, osteopenia, personality changes, gastrointestinal ulceration and hemorrhage, and growth retardation. Dexamethasone, like other steroids, may cause avascular necrosis of bone.

The dosing of dexamethasone, or an equivalent amount of placebo, is specified in Table 9.1. The initial dose (0.3 mg/kg every 12H) is given for a total of 2 days (4 doses) or until hospital discharge, whichever occurs first. Note: Time Zero is defined as the initial dose of study drug and the first 24 hour period begins with the first dose. All subsequent doses and study assessments are scheduled from this time point. Afterward, all subjects will receive the taper as specified in Table 9.1. All study drug should be given by mouth. If medications temporarily cannot be given by mouth (e.g. NPO status for a diagnostic test or altered mental status) then the temporary administration of the study drug by vein during this time period is acceptable. The dose of IV study drug is the same as the oral formulation. The study drug should be given by mouth as soon as oral medications can be tolerated.

Table 9.1 Dose and Frequency of Study Drug

Dose (mg/kg)	Max single Dose (mg)	Frequency	24hr dose (mg/kg)	Duration (days)	
0.3	12	Every 12H	0.6	2 (or hospital discharge)	} “High Dose”
0.3	12	Every 24H	0.3	2	
0.2	8	Every 24H	0.2	2	} “Taper”
0.1	4	Every 24H	0.1	2	

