9.1.2 Dose Modification or Interruption of Study Drug

If the total leukocyte count exceeds $50,000/\text{mm}^3$ during the course of “high dose” study drug (0.3 mg/kg every 12 hours), then the taper will be started immediately. That is, if the leukocyte count exceeds $50,000/\text{mm}^3$, the next dose of study drug (0.3 mg/kg) will be given 24 hours (instead of 12 hours) after the preceding dose of study drug, and the taper should be continued as specified (Table 9.1). If the total leukocyte count exceeds $50,000/\text{mm}^3$ during the “taper”, then the taper will be continued as specified (Table 9.1).

The doses of study drug must be given no more than 60 minutes early or late from the scheduled time (this does not apply to the first dose of study drug which is given within 2 hours of randomization). A protocol deviation form must be completed in the event a dose is outside this time interval or completely missed, however the subject may continue in the study. Missed doses of study drug will not be made up.

Dose Scheduling Modification during the Taper or home administration of study drug will be as follows:

- The Taper dosing may be modified by +/- 4 hours at Hospital Discharge to accommodate the subject's out-patient schedule. A time for each dose should be ascribed each day using the +/- 4 hour window. Then, based on that day's dose time, if it is more than 8 hours late, omit the dose. If a dose is omitted, still use the ascribed time schedule for the next dose.
- Subjects will be instructed to return all unused study drug at the Follow-up clinic visit. Unused study drug will be returned to the site pharmacist for drug accountability according to each institutions policy.

The doses of the study drug will not otherwise be modified or temporarily interrupted. Study drugs may be stopped according to subject discontinuation guidelines (Section 8.4) or because of a severe AE (Section 11.8).

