11.5 Monitoring of Adverse Events

Every AE must be followed to a satisfactory outcome or stabilization of the event, even when this requires a time period beyond the scope of the study (this is particularly applicable to SAEs). Outcome includes information on recovery and any sequelae, as well as specific tests and/or treatments that may have been required and their results. For

a fatal outcome, cause of death and a comment on its possible relationship to the suspected reaction should be provided.

The terms used to define outcome are as follows (outcome of reaction/event at the time of last observation):

- Ongoing,
- Resolved without sequelae,
- Resolved with sequelae, and
- Death.

Actions taken in response to an AE and follow-up results must be recorded in the subject's medical record (this includes follow-up laboratory results). Any treatment administered for the AE must be recorded in the subject's CRF. When subjects are discontinued from the study due to an AE, relevant clinical assessments and laboratory tests will be repeated as necessary until final resolution or stabilization occurs.

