11.7 Subject Discontinuation due to AE(s)

The following criteria will be used to determine whether or not subjects exhibit toxicities of the study drug(s) sufficient to require discontinuation from the study.

We will closely monitor signs, symptoms, and laboratory findings to assess for unexpected toxicities. Oral dexamethasone will be discontinued in any subject who experiences the following:

1. New hypertension (not pre-existing) that requires treatment with antihypertensive medications;
2. Stroke;

3. Gastrointestinal hemorrhage; or
4. Pregnancy.

In addition, subjects will also have dexamethasone discontinued if they become unable to orally ingest dexamethasone or, at the request of the subject, for any reason. In the event that dexamethasone is stopped, subjects will continue to be followed by study personnel to assess for potential side effects of dexamethasone administration.

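### Sections 8.4 and 11.7 use one list of four events both to discontinue the subject and to stop the drug, so a site could end endpoint assessment early; the likely effect is small

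*Protocol*

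**What the plan says.** **Section 8.4.** The list of four events opens with "The following circumstances require discontinuation of subjects". Then: "Subjects who discontinue early from the study will be replaced". For subjects who leave prematurely, the only continued contact named is that they "will be encouraged to maintain the follow-up clinic visits that are scheduled after discharge".

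**Section 11.7.** The same four events appear, introduced as criteria for "toxicities of the study drug(s) sufficient to require discontinuation from the study". The operative sentence is narrower: "Oral dexamethasone will be discontinued in any subject who experiences the following". Subjects then remain under follow-up, with side effects as the stated purpose.

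**Section 9.1.2.** This treats 8.4 as a dosing rule: "Study drugs may be stopped according to subject discontinuation guidelines (Section 8.4) or because of a severe AE (Section 11.8"). Section 11.8 is Pregnancy Reporting; 11.7 is evidently meant.

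**Section 11.5.** "When subjects are discontinued from the study due to an AE, relevant clinical assessments and laboratory tests will be repeated as necessary", until the event resolves or stabilizes.

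**Endpoint schedule.** Section 7.1.1 and the Appendix 3 instructions set the ACS assessment every 4 hours through the hospital stay. Appendix 3 ends the endpoint at the first all-Yes assessment or at discharge, whichever comes first. Section 10.3.2 records duration of hospitalization.

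**Analysis.** Section 13.1 puts every randomized subject in ITT under the assigned arm and uses non-completers' data where possible. Section 13.3.5 makes the primary analysis depend on minimal censoring and names the survival analysis as the sensitivity check if withdrawals before discharge exceed expectation.

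**The concern.** Stopping a drug and leaving a trial are different things, and here one list does both. For a subject discontinued because of an adverse event, the follow-up that 8.4, 11.5 and 11.7 describe is for the event or for side effects. None of the three says that the ACS assessment goes on. A site that takes 8.4 at its word could close out the subject while still in hospital and before the primary endpoint is reached.

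Such stops need not be balanced between arms. Section 9.1.1 says "Potential AEs, especially when given chronically, include hypertension" and goes on to name gastrointestinal hemorrhage. If the assessments end, that subject's primary endpoint depends on discharge time. If discharge time is missing too, a randomized subject has no primary outcome and the ITT comparison is incomplete. An analysis plan cannot recover assessments that were never made, so the rule has to be right in the protocol.

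**Working it through.** **1. The plan's own figure.** Inputs from 13.4: log means 4.25 (placebo) and 3.95 (dexamethasone), log SDs 0.6 and 0.3, two-sided alpha 0.05, power 90%.

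- Normal approximation: n = (1.960 + 1.282)² × (0.6² + 0.3²) / 0.30² = 10.51 × 0.45 / 0.09 = 52.5, so 53 per arm.
- Satterthwaite t-test: power is 0.895 at 53, 0.901 at 54 and 0.911 at 56. The stated 54, and 56 after the allowance of two per arm, are reproduced.

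**2. Likely case: assessments stop, discharge time is kept.** The protocol gives no rate for these events. As an illustration, take two dexamethasone subjects from that arm's longest third and assume discharge trails resolution by 4, 12 or 24 hours.

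- The mean of the upper third of a normal distribution is about 1.09 SD above centre: 3.95 + 1.09 × 0.3 = 4.28 on the log scale, about 72 hours.
- The shift in the arm mean is (2/56) × ln((72 + delay)/72).
- 4 h: (2/56) × 0.054 = 0.002. 12 h: (2/56) × 0.154 = 0.006. 24 h: (2/56) × 0.288 = 0.010.
- Simulated log differences are 0.299, 0.294 and 0.290 against a planned 0.300, in line with the hand figures to within 0.001. Power at 0.05 is 90.7%, 89.9% and 89.0%, against 91.1% with no delay.

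The shift lengthens durations on dexamethasone, so it works against the drug.

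**3. Unfavourable case: discharge time is lost too.** No true effect; two subjects lost at random from the longest third of the dexamethasone arm, none from placebo. Welch t-tests on log duration, without the age and severity terms. False benefit means significant and favouring dexamethasone.

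| Test | SDs 0.6/0.6: no loss, two lost | SDs 0.6/0.3: no loss, two lost |
|---|---|---|
| 0.05, 56 per arm | 2.57%, 3.96% | 2.45%, 3.32% |
| 0.01 (second interim), 56 per arm | 0.50%, 0.87% | 0.52%, 0.72% |
| 0.039 (final), 84 per arm | 1.84%, 2.89% | 1.96%, 2.53% |

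The 84 per arm assumes 112 children plus 56 adults, the most that 7.1.2 anticipates. Total two-sided error at 0.05 with two lost is 5.5% (SDs 0.6/0.6) and 5.1% (0.6/0.3).

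**4. What the inflation depends on** (56 per arm, 0.05; SDs 0.6/0.6, then 0.6/0.3).

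- Two dexamethasone subjects lost at random: 2.40% and 2.49%, no inflation.
- Two lost from the longest third of each arm: 2.48% and 1.79%, none or a reduction.

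Inflation therefore needs loss that is confined largely to one arm, linked to long duration, and extends to discharge time.

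**The case against.** The strongest reply is that the endpoint schedule has no exemption. Section 7.1.1 runs it to discharge, Appendix 3 wants a form even for a missed assessment, and no text orders it stopped. Read with 9.1.2 and the operative sentence of 11.7, the four events can be taken to end dosing and not observation. This stands in part: a reader might infer that the protocol requires endpoint collection to cease, and it does not. What remains is that 8.4 discontinues the subject, and 11.7 itself speaks of leaving the study.

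Exposure is also narrow. The planning log means imply median stays of exp(3.95) = 52 and exp(4.25) = 70 hours, while drug may run 8 days, so many stops would fall in the home taper, after the endpoint is fixed. Pre-existing hypertension, gastrointestinal ulceration or bleeding, and pregnancy are excluded (8.2), and 9.1.1 ties the listed effects especially to chronic use. This stands.

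Three further readings are tempting and not supported:

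- **That rebound data rest on voluntary visits.** Hospitalization is a serious adverse event (11.3), reported until 30 days after the last dose (11.6.1). Among follow-up data, mainly the visit-2 radiograph and pulmonary function tests need attendance, and attendance is only encouraged for all subjects (9.4).
- **That replacement removes subjects from the analysis.** Section 13.1 keeps every randomized subject in ITT.
- **That there is no analysis for early withdrawal.** Section 13.3.5 plans one. It can use censored times, although it would not cure censoring related to outcome.

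On the other side, a 4 to 24 hour lag may be too short after a stroke or hemorrhage that itself prolongs the stay. Assumed delays of 72 and 120 hours in two subjects give power of about 84% and 80%. That is still a loss of power against dexamethasone, not a false claim for it.

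**Conclusion.** The contradiction is real and should be corrected: the same four events discontinue the subject in 8.4, and in 11.7 are announced as study discontinuation but only stop the drug. The statistical consequence is conditional and probably small. It requires a site to apply 8.4 literally to a subject still in hospital with unresolved ACS.

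In the likely case discharge time survives, the endpoint becomes length of stay, and with two affected dexamethasone subjects and a 4 to 24 hour lag the log difference is 0.290 to 0.299 in place of 0.300, with power of 89-91%. A reader might infer that the trial's type I error is compromised. The documents do not support that: the rise in false benefit from 2.5% to 3.3-4.0% at two-sided 0.05 needs discharge time to be lost as well, in two long-stay dexamethasone subjects and no placebo subjects.

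All of these sizes rest on assumed event counts and delays. The count of two borrows the whole per-arm withdrawal allowance in 13.4, which was not set for these events.

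**What to change.** - In 8.4 and 11.7, state that the four events stop study drug only, and remove the wording that makes them grounds for leaving the study.
- State that the 4-hourly ACS assessments to discharge, the time of discharge and both follow-up visits continue for every randomized subject unless consent to data collection is withdrawn.
- State in 8.4 that a replacement is additional enrolment and that no randomized subject leaves the ITT population.
- Editorial only: in 9.1.2, change the reference to 11.8 to 11.7.

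The clinical triggers for stopping drug do not change, and neither does the sample size. The cost is wording in three sections and a few more forms for subjects who are off drug; the inpatient assessments are already scheduled.

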9 TREATMENT OF SUBJECTS

9.1 Treatments

9.1.1 Description of Study Drug and Dosing Regimen

Dexamethasone is a commercially available synthetic corticosteroid hormone that is used primarily as an anti-inflammatory agent. It is available in tablets (several manufacturers), and as a solution for IV injection (several manufacturers).

Potential AEs, especially when given chronically, include hypertension, hyperphagia, weight gain, hyperglycemia, striae, acne, osteopenia, personality changes, gastrointestinal ulceration and hemorrhage, and growth retardation. Dexamethasone, like other steroids, may cause avascular necrosis of bone.

The dosing of dexamethasone, or an equivalent amount of placebo, is specified in Table 9.1. The initial dose (0.3 mg/kg every 12H) is given for a total of 2 days (4 doses) or until hospital discharge, whichever occurs first. Note: Time Zero is defined as the initial dose of study drug and the first 24 hour period begins with the first dose. All subsequent doses and study assessments are scheduled from this time point. Afterward, all subjects will receive the taper as specified in Table 9.1. All study drug should be given by mouth. If medications temporarily cannot be given by mouth (e.g. NPO status for a diagnostic test or altered mental status) then the temporary administration of the study drug by vein during this time period is acceptable. The dose of IV study drug is the same as the oral formulation. The study drug should be given by mouth as soon as oral medications can be tolerated.

Table 9.1 Dose and Frequency of Study Drug

Dose (mg/kg)	Max single Dose (mg)	Frequency	24hr dose (mg/kg)	Duration (days)	
0.3	12	Every 12H	0.6	2 (or hospital discharge)	} “High Dose”
0.3	12	Every 24H	0.3	2	
0.2	8	Every 24H	0.2	2	} “Taper”
0.1	4	Every 24H	0.1	2	

9.1.2 Dose Modification or Interruption of Study Drug

If the total leukocyte count exceeds $50,000/\text{mm}^3$ during the course of “high dose” study drug (0.3 mg/kg every 12 hours), then the taper will be started immediately. That is, if the leukocyte count exceeds $50,000/\text{mm}^3$, the next dose of study drug (0.3 mg/kg) will be given 24 hours (instead of 12 hours) after the preceding dose of study drug, and the taper should be continued as specified (Table 9.1). If the total leukocyte count exceeds $50,000/\text{mm}^3$ during the “taper”, then the taper will be continued as specified (Table 9.1).

The doses of study drug must be given no more than 60 minutes early or late from the scheduled time (this does not apply to the first dose of study drug which is given within 2 hours of randomization). A protocol deviation form must be completed in the event a dose is outside this time interval or completely missed, however the subject may continue in the study. Missed doses of study drug will not be made up.

Dose Scheduling Modification during the Taper or home administration of study drug will be as follows:

- The Taper dosing may be modified by +/- 4 hours at Hospital Discharge to accommodate the subject's out-patient schedule. A time for each dose should be ascribed each day using the +/- 4 hour window. Then, based on that day's dose time, if it is more than 8 hours late, omit the dose. If a dose is omitted, still use the ascribed time schedule for the next dose.
- Subjects will be instructed to return all unused study drug at the Follow-up clinic visit. Unused study drug will be returned to the site pharmacist for drug accountability according to each institutions policy.

The doses of the study drug will not otherwise be modified or temporarily interrupted. Study drugs may be stopped according to subject discontinuation guidelines (Section 8.4) or because of a severe AE (Section 11.8).

9.1.3 Packaging, Labeling, and Blinding of Study Drug

All study drug (active and placebo) will be prepared by the central study pharmacist at Children's Medical Center Dallas, Dallas TX, and shipped to participating centers' pharmacies for dispensing. Oral study drug will be available only in capsule formulation (over-encapsulated tablets). Placebo and active study drug capsules will appear identical. Oral study drug will not be available in a liquid preparation because of the inability to produce an identically flavored placebo formulation. IV placebo will be normal saline. The active and placebo IV study drugs will be clear solutions delivered in pre-filled syringes.

Study drug will be delivered to the inpatient ward in single-dose units for each individual subject and labeled in accordance with guidelines for all inpatient medications. The label will indicate the name of the drug to be either “ACS oral study drug” or, if needed, “ACS IV study drug”.

9.1.4 Return and Destruction of Study Drug(s)

Unused inpatient study drug will be returned to the participating centers’ hospital pharmacies for disposal according to their standard operating procedures.

9.1.5 Guidelines for Supportive Care

Antimicrobial therapy: All subjects will receive antimicrobial therapy directed against the most commonly isolated organisms in ACS: *Chlamydia pneumoniae*, *Mycoplasma pneumoniae*, *Staphylococcus aureus* (coagulase positive), *Streptococcus pneumoniae*, and *Mycoplasma hominis*. Cefuroxime (50 mg/kg/dose [maximum 1500 mg] IV every 8 hours) and azithromycin (10 mg/kg/dose [maximum 500 mg] by mouth (p.o.) on day 1, then 5 mg/kg/dose [maximum 250 mg] p.o. on days 2 through 5) are recommended antibiotics after a blood culture is obtained. The choice of the antibiotic is at the discretion of the local physician/investigator.

Antimicrobial therapy may be altered appropriately if a specific organism is isolated.

Intravenous fluids: IV fluids will be infused to correct any dehydration and to maintain adequate hydration. D5 0.45 NS with 10 mEq/L potassium chloride will initially be infused at 1 to 1.5 times the calculated maintenance rate (a higher rate may be needed to correct any dehydration) and continued until adequate hydration can be maintained by drinking. The daily maintenance fluid volume is calculated by adding 100 ml/kg/day for the first 10 kg of body weight, 50 ml/kg/day for the second 10 kg of body weight, and 20 ml/kg/day for weight greater than 20 kg. This total daily volume is divided by 24 (hours) to arrive at the hourly infusion rate in ml/hour (the suggested maximum infusion rate is 125 ml/hr). *The rate and composition of the fluid may be modified at the discretion of the attending physician, with the caveat that over-hydration is to be avoided.*⁵⁹

Respiratory therapy: Supplemental oxygen will be administered to maintain a peripheral oxygen saturation of at least 90% by pulse oximetry. Oxygen will be discontinued when the subject maintains a peripheral oxygen saturation of at least 92%, or a documented baseline value, in room air. Arterial blood gas measurements may be performed at the discretion of the attending physician. All subjects should perform incentive spirometry with 10 breaths every two hours from 8 am to 10 pm and every two hours while awake at night.⁷⁷ Young children who are unable to perform incentive spirometry will perform a similar age-appropriate activity, such as blowing bubbles. Chest physiotherapy (CPT) may be prescribed at the discretion of the attending physician. Nebulized bronchodilators may be prescribed at the discretion of the attending physician, and they should be strongly considered for subjects with wheezing or clinical evidence of lower airway obstruction.

Gastrointestinal prophylaxis: All subjects should receive empiric prophylactic treatment with an H₂- (histamine₂-) receptor antagonist, such as ranitidine (2-4 mg/kg/day divided BID with a maximum daily dose of 300 mg), for at least the 8 days of study drug treatment. A different H₂-receptor antagonist or a proton pump inhibitor may be used instead of ranitidine at the treating physician's discretion.

Analgesia: Subjects who are in pain will be treated with ibuprofen (10 mg/kg/dose [maximum 600 mg] p.o. every 6h) and if needed acetaminophen/codeine (1 mg/kg/dose of codeine p.o. every 4-6h). The ibuprofen and acetaminophen/codeine may be alternated every 2 hours. If pain is severe, or oral analgesia is not sufficient, morphine (0.1 mg/kg/dose IV every 2h prn) can be given. The use of continuous infusion morphine or other parenteral opioid analgesics requires caution. Dosing and selection of analgesics can be modified at the discretion of the treating physician to safely achieve optimal pain control.

Transfusion: Attending physicians may prescribe transfusion outside of these guidelines if deemed clinically appropriate. All transfused packed red blood cells (PRBCs) will have extended antigen matching for C, D, E, and Kell, except in the case of emergency.

- **Simple transfusion** of PRBCs will be given when the hemoglobin (Hgb) concentration is ≤ 5 g/dL or it has decreased 2 g/dL or more from the subject's baseline Hgb (recorded in the individual's database or medical record). Simple transfusion will also be given when the Hgb concentration has decreased 1 g/dL or more from the baseline Hgb if the subject has hypoxemia requiring supplemental oxygen. The expected post-transfusion Hgb should not exceed 11 g/dL to avoid hyperviscosity and the possibility of worsening the ACS or causing a stroke.
- **Exchange transfusion** is indicated for any of the following: extensive bilateral pulmonary disease, hypoxemia not corrected by supplemental oxygen, or rapid clinical deterioration. Automated red cell exchange (erythrocytapheresis) will be performed unless technical difficulties necessitate a manual exchange. The goal of exchange transfusion is a Hgb of 9 – 10 g/dL and a % Hgb S of 30% or less.

Other: An irritant or osmotic laxative is recommended for all subjects who receive opioids because of the expected constipation. Diphenhydramine or hydroxyzine may be given as needed for pruritus.

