Criteria for Evaluation: Efficacy: Primary Endpoint: The duration of signs and symptoms of ACS or duration of hospitalization, whichever is less. The duration of signs and symptoms of ACS is defined as the interval between study entry and the time at which tachypnea, hypoxemia, increased work of breathing, and thoracic pain have resolved and supplemental oxygen and ventilatory support are no longer utilized. Secondary Endpoints: Clinical endpoints include: rating of pain, duration of hospitalization, supplemental oxygen, hypoxemia, and fever, number of transfusions, quantification of opioid use, rebound hospitalizations, pulmonary radiographic findings, and pulmonary function testing results. Laboratory endpoints include: VCAM ₁ , ICAM ₁ , P-selectin, L-selectin, vWF multimers, endothelial and monocyte microparticles, WBTF, NO, and sPLA ₂ . Safety: Adverse events (AEs), vital signs, physical examination, concomitant medications, complete blood count (CBC), urine output and daily fluid balance, blood culture, pulse oximetry, reticulocyte count, and baseline and interim history.
Study Design: Phase III randomized, double-blind, controlled clinical trial with two arms.
Study Population: Individuals of both genders 5 years of age and older with Hgb SS and Hgb Sβ ⁰ are eligible.
Major Inclusion Criteria: New episode of ACS; diagnosis of ACS within preceding 24 hours; and provision of informed consent.
Major Exclusion Criteria: Prior participation in this study; corticosteroids contraindicated for comorbid conditions; corticosteroid treatment in preceding 2 weeks.
Clinical and Laboratory Evaluations: The primary endpoint is the duration of signs and symptoms ACS (resolution of tachypnea, hypoxemia, increased work of breathing, and thoracic pain as well as the cessation of medical interventions to support respiration). Other clinical evaluations include subject pain, requirement for opioid analgesics, number of transfusions, use of supplemental oxygen, duration of hypoxemia, duration of hospitalization, and duration of fever. A chest radiograph and spirometry will be performed at a follow-up visit. A panel of biomarkers related to endothelial activation, coagulation, and nitric oxide (NO) bioavailability will be obtained at several time points.
Sample Size: At least 56 subjects with SCD who are hospitalized for ACS.

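### The analgesia guideline sets ibuprofen at every 6 hours, but the alternation it permits, read literally, repeats ibuprofen every 4 hours (0% to 50% more in 24 hours)

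*Protocol*

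**What the plan says.** The analgesia paragraph of Protocol section 9.1.5 gives a frequency for each oral drug. Subjects in pain receive "ibuprofen (10 mg/kg/dose [maximum 600 mg] p.o. every 6h"), and "if needed acetaminophen/codeine (1 mg/kg/dose of codeine p.o. every 4-6h"). The next sentence reads: "The ibuprofen and acetaminophen/codeine may be alternated every 2 hours".

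The paragraph then provides a step-up: "If pain is severe, or oral analgesia is not sufficient, morphine" can be given intravenously. It ends with a discretion clause: "Dosing and selection of analgesics can be modified at the discretion of the treating physician to safely achieve optimal pain control".

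Ibuprofen has a per-dose ceiling but no daily maximum. Nothing says that each drug keeps its own interval while the two are alternated.

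**The concern.** The alternation sentence directly follows the stated intervals and does not agree with one of them. A nurse or pharmacist who alternates as written gives ibuprofen every 4 hours. One who follows the preceding sentence gives it every 6 hours.

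What is at stake is dosing safety, not inference. The trial takes "Individuals of both genders 5 years of age and older". Half of the subjects are allocated to dexamethasone, for which section 9.1.1 lists gastrointestinal ulceration and hemorrhage as potential adverse events. Gastrointestinal hemorrhage also requires discontinuation under sections 8.4 and 11.7. An unintended shortening of the interval for a non-steroidal anti-inflammatory drug works against the care the protocol otherwise takes over gastrointestinal risk.

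**Working it through.** **Inputs, all from Protocol section 9.1.5.** Ibuprofen 10 mg/kg per dose, maximum 600 mg, every 6 h. Acetaminophen/codeine every 4 to 6 h, if needed. Alternation step 2 h.

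**Stated ibuprofen schedule.** Doses at 0, 6, 12 and 18 h: 24/6 = 4 doses. Amount 4 × 10 = 40 mg/kg; ceiling 4 × 600 = 2,400 mg. The protocol prints no daily total, so this is derived from its interval and dose.

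**Strict alternation.** Same-drug interval = 2 drugs × 2 h = 4 h, against 6 h stated. Starting with ibuprofen:
- ibuprofen at 0, 4, 8, 12, 16, 20 h: 6 doses, 60 mg/kg, ceiling 3,600 mg;
- acetaminophen/codeine at 2, 6, 10, 14, 18, 22 h, which is within its stated range.

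Excess over a full day = 6/4 − 1 = 50%.

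**Part-day alternation, then back to every 6 h.** Count ibuprofen doses from 0 h up to but not including 24 h. Let the last alternated ibuprofen dose fall at 4k h. There are k + 1 doses up to that point, and ceil((24 − 4k)/6) − 1 further doses at 6-hour steps. The total is k + ceil((24 − 4k)/6).

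| Last alternated ibuprofen dose | Ibuprofen times (h) | Doses | mg/kg | Ceiling (mg) | Excess |
|---|---|---|---|---|---|
| 0 h | 0, 6, 12, 18 | 4 | 40 | 2,400 | 0% |
| 4 h | 0, 4, 10, 16, 22 | 5 | 50 | 3,000 | +25% |
| 8 h | 0, 4, 8, 14, 20 | 5 | 50 | 3,000 | +25% |
| 12 h | 0, 4, 8, 12, 18 | 5 | 50 | 3,000 | +25% |
| 16 h | 0, 4, 8, 12, 16, 22 | 6 | 60 | 3,600 | +50% |
| 20 h | 0, 4, 8, 12, 16, 20 | 6 | 60 | 3,600 | +50% |

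The doses after alternation stops have to be counted. Leaving them out would make a short spell of alternation look free of any daily excess, but one ibuprofen dose brought forward from 6 h to 4 h is enough to fit a fifth dose into the 24 hours.

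**Staggered reading.** Each drug keeps a 6-hour interval and acetaminophen/codeine starts 2 h after ibuprofen: ibuprofen at 0, 6, 12, 18 h and acetaminophen/codeine at 2, 8, 14, 20 h. Ibuprofen stays at 4 doses, 0% excess. The merged times 0, 2, 6, 8, 12, 14, 18, 20 h have gaps of 2, 4, 2, 4, 2, 4, 2 h, so a dose is not given at every 2-hour step.

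**Check of a 3-hour step.** Ibuprofen at 0, 6, 12, 18 h and acetaminophen/codeine at 3, 9, 15, 21 h. Each drug recurs every 6 h, both stated intervals are met, and the excess is 0%.

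**The case against.** The strongest reply is that this is an ambiguity and not an error. The only explicit ibuprofen frequency is every 6 hours, and the alternation sentence neither restates nor replaces it. A sensible clinician may take it as leave to give the second drug 2 hours after the first with both intervals still binding. That reading is available and costs nothing in dose. But it respects the 6-hour interval only by setting aside the literal 2-hour step, and the paragraph gives no rule for choosing between them.

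The second reply is that the scheme is permissive, acetaminophen/codeine is given only if needed, inadequate oral relief leads to morphine, and the physician may change any dose. All of this stands and keeps the weight low. It does not settle the conflict: discretion allows departure from the guideline but does not say which of two adjacent statements is the guideline.

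The third reply is that gastrointestinal risk is already managed. "All subjects should receive empiric prophylactic treatment with an" H2-receptor antagonist (section 9.1.5), and section 8.2 excludes patients with "esophageal or gastrointestinal ulceration or bleeding". This also stands.

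Three stronger inferences are tempting and are not supported:
- *The protocol prescribes a 50% ibuprofen excess.* No subject is required to receive the 4-hour schedule, and the 50% figure needs strict alternation with an ibuprofen dose at 16 hours or later.
- *The higher amounts are shown to be harmful.* The document gives no ibuprofen daily limit to set 60 mg/kg or 3,600 mg against.
- *The treatment comparison is biased.* The guideline is the same in both blinded arms.

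**Conclusion.** The point holds as a minor safety-wording correction. The plain reading of the alternation sentence gives an ibuprofen interval of 4 hours against the 6 hours stated immediately before it. Over 24 hours the excess is 0% under staggering, 25% when strict alternation ends with an ibuprofen dose at 4 to 12 hours, and 50% when it ends at 16 hours or later.

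These figures assume that alternation starts with ibuprofen at 0 hours, that 6-hourly dosing resumes from the last alternated ibuprofen dose, that no dose is skipped, and that the full 10 mg/kg (or the 600 mg ceiling) is given each time. How often sites would follow the literal schedule cannot be known from the document. Sample size, alpha and the primary analysis are untouched. The correction should be made because it is simple and concerns a dosing instruction that applies to children, not because harm has been shown.

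**What to change.** Replace the alternation sentence in section 9.1.5 with one of two wordings:
- *The two drugs may be alternated every 3 hours (each drug every 6 h).* This is the simpler text, but it gives up 4-hourly acetaminophen/codeine while the drugs are alternated.
- *The two drugs may be offset by 2 hours, with ibuprofen no more often than every 6 h (at most 4 doses per 24 h) and acetaminophen/codeine no more often than every 4 h.* This keeps the full acetaminophen/codeine range. If that drug is given every 4 hours from 2 h, both drugs fall together at 6 h and 18 h, so the doses no longer strictly alternate, though both intervals are met.

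The physician discretion clause stays as it is. The cost is one sentence in the protocol and a clarification memo to sites, with no change to sample size, alpha or analysis.
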